- IMP accountability based on blisters
- ECG (at about the same time as but before the PK sample)
- Vital signs (blood pressure (BP) and heart rate)
- Urine pregnancy test
- Urinary protein dipstick
- Blood samples for haematology, coagulation parameters, chemistry, hormones (E2, LH and progesterone (P4))
- Pre-dose PK sample (the time of study medication administration on previous 4 days and time of PK sampling will be recorded)
- Contraception dispensing (if applicable) and counselling
- Prescribe/dispense permitted analgesics as rescue medication
- Dispense calcium and vitamin D supplementation

- Dispensing via IWRS of one new kit of linzagolix

The subject will take her daily dose of study medication at the study site from the newly dispensed linzagolix/placebo kit, and from the ABT/placebo kit dispensed at the Month 6 visit.

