10.2.1.3 Study visit: Month 9 (Day 253 ± 3 days)

The following tests and evaluations will be performed:

- eDiary completion compliance check
- ePRO and ClinRO completion, ideally before any other procedures or assessments: EHP-30, EQ-5D-5L, PROMIS, mPGIS, PGIC, HRUQ, HRPQ (mPGIS and PGIC must be completed last)
- Concomitant treatments recording
- AE recording
- Completion of the paper C-SSRS questionnaire (version for "already enrolled subjects" (see Appendix R) for patients responding to the C-SSRS for the first time during the study, or version "since last study visit" (see Appendix S) for patients for whom the C-SSRS was completed at the previous study visit)
- IMP accountability based on blisters
- ECG (at about the same time as but before the PK sample)
- Physical examination, including weight recording
- Vital signs (BP and heart rate)
- Urine pregnancy test
- Gynecological examination
- TVUS of the uterus
- Urinary protein dipstick
- Fasting (overnight) blood samples for haematology, coagulation parameters, chemistry, lipids, hormones (E2, LH, P4 and sex hormone-binding globulin (SHBG)) and bone biomarkers
- Pre-dose PK sample (the time of dose administration on previous 4 days and time of PK sampling will be recorded)
- BMD assessed by DXA for femoral neck, hip and spine for subjects who met the following criterion at any site on the Month 6 DXA scan: -2.5 < Z-score ≤ -1.5
- Contraception dispensing (if applicable) and counselling
- Prescribe/dispense permitted analgesics as rescue medication
- Dispense calcium and vitamin D supplementation

- Dispensing via IWRS of one new kit of linzagolix/placebo and one new kit of ABT/placebo

The subject will take her daily dose of study medication at the study site from the newly dispensed kits.

10.2.1.4 Study visits: Month 10 (Day 281 ± 3 days) and Month 11 (Day 309 ± 3 days)

The following tests and evaluations will be performed :

- eDiary completion compliance check
- ePRO and ClinRO completion, ideally before any other procedures or assessments: mPGIS, PGIC, HRUQ, HRPQ with mPGIS and PGIC completed last
- Concomitant treatments recording
- AE recording
- Completion of the paper C-SSRS questionnaire (version for "already enrolled subjects" (see Appendix R) for patients responding to the C-SSRS for the first time during the study, or version "since last study visit" (see Appendix S) for patients for whom the C-SSRS was completed at the previous study visit)
- IMP accountability based on blisters

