- ECG (at about the same time as but before the PK sample)
- Vital signs (BP and heart rate)
- Urine pregnancy test
- Urinary protein dipstick
- Blood samples (fasting not required) for haematology, coagulation parameters, chemistry, hormones (E2, LH and P4)
- Pre-dose PK sample (the time of study medication administration on previous 4 days and time of PK sampling will be recorded)
- Contraception dispensing (if applicable) and counselling
- Prescribe/dispense permitted analgesics as rescue medication
- Dispense calcium and vitamin D supplementation
- Dispensing via IWRS of one new kit of linzagolix/placebo

The subject will take her daily dose of study medication at the study site from the newly dispensed linzagolix/placebo kit, and from the ABT/placebo kit dispensed at the Month 9 visit.

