10.4.8 Laboratory parameters

Haematology, coagulation parameters and chemistry will be assessed at each visit during the Treatment Period, as well as at Month 1 ExFU and Month 3 ExFU visits. Fasting lipids will be assessed at Month 9, Month 12 and Month 3 ExFU visits.

E2, P4 and LH will be assessed at each visit during the treatment period, as well as at M1 ExFU and M3 ExFU visits. Serum levels of SHBG will be assessed at Month 9 and Month 12 visits.

Overnight fasting is required for Months 9, 12 and Month 3 ExFU visits.

Blood samples will be analyzed by the central laboratory. Details of blood sampling process, sample handling and shipment are described separately in a laboratory manual provided by the central laboratory. Central laboratory reference ranges will be filed in the investigator site file and in the trial master file. All laboratory results except E2, P4, LH and SHBG levels will be assessed by the Investigator/sub-Investigator. Clinically significant abnormalities compared to main study baseline status will be reported as AEs in the eCRF. E2, P4, LH and SHBG levels will not be communicated to keep the operational team and the sites blinded to treatment administration.

The laboratory parameters are listed in Appendix M.

There may be some additional laboratory parameters to be analysed as requested by the medical monitor in order to follow-up on existing abnormalities.

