Appendix A. Schedule of study assessments – Treatment Period

¹ All visits should take place at the end of the defined period (i.e. M7 visit should be scheduled at the end of Month 7, M8 visit should be scheduled at the end of Month 8, etc.). All visit dates should be calculated from the date of Day 1 visit (in the main study). A month is defined as 28 days/4 weeks. Visits should be scheduled ± 3 days (-3/+ 2 days for Month 7 visit) from the calculated date.

² All Month 6 assessments except informed consent and inclusion/exclusion criteria would have been performed as part of the main study (18-OBE2109-002 - Edelweiss 2).

³ ECG should be performed at about the same time but before the PK sample

 $^4~$ If endometrium thickness in TVUS is $\leq 5~$ mm, no endometrial biopsy will be necessary.

⁵ Overnight fasting is required.

 $^{6}\,$ Only for subjects who met the following criterion at any site on the M6 DXA scan: -2.5 < Z-score \leq -1.5

Schedule of study	assessments -	Treatment 1	Period ((cont'd)
e e e				· /

Schedule of study assessments – Treatment Period							
Timing ¹	Treatment Period						
	M6 ²	M7	M8	M9	M10	M11	M12
IMP accountability	X	X	X	X	X	X	X
Dispense linzagolix/placebo kit	X	X	x	x	x	X	
Dispense ABT/placebo kit	X			х			
EHP-30, EQ-5D-5L and PROMIS ³	x	x		x			x
mPGIS, PGIC, HRUQ and HRPQ ³	X	х	х	х	X	х	Х
SSIQ and PSIQ ³	x						X
Blood sample for PK ⁴	X	х	х	х	X	X	Х
E2, LH, P4	X	X	x	X	X	x	x
SHBG	X			x			X
Bone biomarkers	X			х			Х

¹ All visits should take place at the end of the defined period (i.e. M7 visit should be scheduled at the end of Month 7, M8 visit should be scheduled at the end of Month 8, etc.). All visit dates should be calculated from the date of Day 1 visit (in the main study). A month is defined as 28 days/4 weeks. Visits should be scheduled ± 3 days from the calculated date.

² All Month 6 assessments except informed consent and inclusion/exclusion criteria would have been performed as part of the main study.

³ ClinROs (PSIQ and HRUQ) will be administered to the subject by the site staff and the responses will be filled in the eDiary. ePROs (EHP-30, EQ-5D-5L, PROMIS, PGIS, PGIC, HRPQ and SSIQ) will be filled in by the subject in the eDiary.

⁴ PK samples should be taken after the ECG and before the daily dose of IMP.

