Appendix M. Laboratory parameters

Routine Haematology	Blood Chemistry
Haemoglobin	Sodium
Haematocrit	Potassium
RBC count	Calcium
WBC count	Phosphate
Neutrophils	Creatinine
Lymphocytes	Bilirubin total
Monocytes	Indirect Bilirubin
Eosinophils	Total protein
Basophils	Albumin
Thrombocytes	AST
MCV	ALT
MCH	γGT
MCHC	Alkaline phosphatase
APTT	Creatine Kinase
INR	LDH
РТ	HDL, LDL, total cholesterol, and LDL/HDL ratio, triglycerides
	Glucose
	Urea and uric acid

Urinary protein dipstick

Hormones

E2, LH, P4, SHBG

All the above listed tests are to be performed at the frequencies indicated in Appendix A and Appendix B. All above listed blood tests will be performed by a central laboratory. Please consult the central laboratory instructions manual for the preparation and handling of the blood samples to be drawn to perform these tests.

Bone markers

Blood samples for exploratory bone biomarkers such as, but not limited to, collagen type 1 β -carboxy-telopeptide (CTx), procollagen 1 Intact N-Terminal (P1NP), bone-specific alkaline phosphatase (B-ALP) and osteocalcin will be collected as part of clinical chemistry.

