#### 4.8.4. Laboratory Data

Clinical laboratory values will be expressed using conventional SI units.

Hematology, coagulation parameters, chemistry and lipids were assessed at screening and at each visit during the extension treatment period (from M7 to M12), as well as at the M1 ExtFU and M3 ExtFU visits.

E2, progesterone (P4) and LH were assessed at each visit during the extension treatment period (from M6 to M12), as well as at M1 ExtFU and M3 ExtFU visits.

Serum levels of sex hormone-binding globulin (SHBG) were assessed on Month 6, Month 9 and Month 12 visits.

Blood samples were to be analyzed by the central laboratory. Due to the covid-19 situation, some samples may be collected by local laboratories.

For Hematology, coagulation parameters, chemistry and lipids, the actual value, change from baseline and change from baseline 2 (only for the subjects who are in the placebo arm in the main study) will be summarized for each visit for each treatment group. In the event of repeated values, the last non-missing value per study day/time will be used.

Evaluation of shifts for changes from baseline and for changes from baseline 2 (only for the subjects who are in the placebo arm in the main study) to all visits according to the normal ranges with categories "Low", "Normal", "High" and according to normal/abnormal/abnormal clinically significant information collected otherwise, will be provided.

For Liver Function Test (LFT) parameters (ALT, AST, ALP, total bilirubin, direct bilirubin, indirect bilirubin, GGT, LDH, albumin and Creatine Kinase), evaluation of shifts for changes from baseline will be extended by the worst (highest) on-treatment value (including unscheduled assessments) according to the normal ranges with categories "Low", "Normal", "High" will be provided.

For the lipid panel (Triglycerides, HDL, LDL, Total Cholesterol, LDL/HDL ratio), the percent change from baseline and the percent change from baseline 2 (only for the subjects who are in the placebo arm in the main study) to each on-study visit will also be summarized.

For serum levels of P4, SHBG and LH, only the actual values at each time point will be summarized. Note: in the event of repeated values, the last non-missing value per study day/time will be used.

Note that no serum levels of E2 is measured for subjects in extension study due to the early termination study.

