# Cytel

## Statistical Analysis Plan

Sponsor:	ObsEva		
Protocol:	19-OBE2109-00	5	
Document Version No.:	1.0	Document Date:	18-MAY-2021

- LDL ≥ 190 mg/dL
- HDL < 40 mg/dL

will be reported at each visit.

Shift tables from baseline and shift tables from baseline 2 (only for the subjects who are in the placebo arm in the main study) to each visit will be provided for the following LDL and Triglycerides categories (after rounding to integer values if necessary).

LDL:

- 0: ≤ 130 mg/dL
- 1: 131 to 159 mg/dL
- 2: 160 to 189 mg/dL
- 3: ≥ 190 mg/dL

Triglycerides:

- 0: ≤ 150 mg/dL
- 1: 151 to 300 mg/dL
- 2: 301 to 500 mg/dL
- 3: 501 to 1000 mg/dL
- 4: >1000 mg/dL

All laboratory data will be provided in data listings. Day 1 Serum levels of the anti-müllerian hormone (AMH) and fasting glucose will be included in the listings.

A subset listing will be presented for all abnormal clinically significant laboratory values.

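### SAP 4.8.4 tabulates glucose change and shifts at every visit without regard to fasting, so for former placebo subjects a meal effect can look like an on-treatment rise

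*SAP*

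**What the plan says.** **Panel.** Protocol Appendix M lists glucose under blood chemistry and states: "All the above listed tests are to be performed at the frequencies indicated in Appendix A and Appendix B". Section 10.4.8 has chemistry drawn at each treatment visit and at Months 1 and 3 ExFU.

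**Fasting.** Protocol 10.4.8 says: "Overnight fasting is required for Months 9, 12 and Month 3 ExFU visits". In Appendix A the clinical laboratory row carries footnote 5, "Overnight fasting is required", at Months 6, 9 and 12. The visit sections agree. Month 9 (10.2.1.3) calls for "Fasting (overnight) blood samples for haematology, coagulation parameters, chemistry, lipids, hormones", and Month 12 and Month 3 ExFU are worded the same way. Months 7 and 8 (10.2.1.2) ask for "Blood samples for haematology, coagulation parameters, chemistry, hormones (E2, LH and progesterone (P4"), with no fasting instruction, and Month 1 ExFU is likewise silent. Months 10 and 11 (10.2.1.4) are explicit: "Blood samples (fasting not required) for haematology, coagulation parameters, chemistry, hormones (E2, LH and P4").

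**Analysis.** SAP 4.8.4 treats all chemistry alike. By visit and treatment group it gives: "the actual value, change from baseline and change from baseline 2 (only for the subjects who are in the placebo arm in the main study". It also provides shifts by normal range to all visits. Its one sentence on glucose concerns a listing: "Day 1 Serum levels of the anti-müllerian hormone (AMH) and fasting glucose will be included in the listings". SAP 4.2.11 defines Baseline 2 as the last assessment before the first active extension dose, for main-study placebo subjects only.

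**The concern.** Glucose depends on whether the subject has eaten. A table that takes change from a fasting value to a possibly fed one mixes a sampling condition with any drug effect. In the two groups that switch from placebo, Months 7 and 8 are the first readings on active drug, so a meal effect there would coincide with the start of linzagolix, with or without add-back, and could fall away at Month 9 when fasting is again required.

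All extension subjects are on active drug, and both dose groups follow the same visit schedule. No concurrent placebo arm would show the pattern to be an artefact, and comparing the two doses would not reveal it either. After early termination the SAP concentrates on safety, and change in biochemistry from baseline is a stated safety endpoint (SAP 2.5.3), so these tables will carry the laboratory conclusions.

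**Working it through.** The plan states no figure for this point, so there is none to reproduce. The check is a count of visits, followed by an illustration on assumed inputs.

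**1. Visits at which the SAP can tabulate post-baseline chemistry**

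| Visit | Fasting instruction | Source (protocol) |
|---|---|---|
| Month 6 (normal source of Baseline 2) | required | Appendix A, footnote 5 |
| Months 7, 8 | none given | 10.2.1.2 |
| Month 9 | required | 10.2.1.3, 10.4.8 |
| Months 10, 11 | stated as not required | 10.2.1.4 |
| Month 12 | required | 10.2.1.5, 10.4.8 |
| Month 1 ExFU | none given | 10.2.2.1 |
| Month 3 ExFU | required | 10.2.2.2, 10.4.8 |

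- On treatment: 6 visits (Months 7 to 12), of which 4 (Months 7, 8, 10, 11) have no fasting requirement.
- All post-baseline chemistry visits: 6 + 2 = 8, of which 4 + 1 = 5 have no fasting requirement.

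**2. Which baseline is known to be fasting**

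For former placebo subjects, Baseline 2 is normally the Month 6 draw, which is fasting. The mismatch is therefore established for that comparison. The main-study baseline draw is not described in these documents. The SAP's mention of a Day 1 fasting glucose suggests that it was fasting but does not settle it.

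**3. Visit labels do not identify fasting samples**

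Subjects who stop treatment early undergo the Month 12 procedures (Protocol 10.7.2, SAP 4.2.7), which include a fasting draw. SAP 4.2.10 assigns such a sample to a visit within ±14 days if the assessment was planned there and no other is in the window. Chemistry is planned at every treatment visit, so a fasting discontinuation sample can become the Month 7, 8, 10 or 11 value. An unscheduled sample can likewise fill a Month 9 or Month 12 row with no check on fasting.

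**4. Illustration of size (all inputs assumed)**

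Let f be the share of subjects who had eaten, d the meal shift in SDs of fasting glucose, and g the distance of the upper normal limit above the fasting mean in SDs. With normal distributions and no drug effect:

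- mean bias = f × d
- P(High) = (1 − f)[1 − Φ(g)] + f[1 − Φ(g − d)]

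The ranges taken are f = 0.25 to 1, d = 0.5 to 2 and g = 1.5 to 2.

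- Mean bias: from 0.25 × 0.5 = 0.125 SD to 1 × 2 = 2 SD.
- g = 2: 2.3% High when fasting, rising to between 3.4% (f = 0.25, d = 0.5) and 50% (f = 1, d = 2).
- g = 1.5: 6.7% High when fasting, rising to between 9.0% and 69%.
- A middle case, f = 0.5, d = 1, g = 2: 0.5 × 0.0228 + 0.5 × 0.1587 = 0.091, or 9.1%.

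On these assumptions the bias is always upward, but the range is too wide to give a usable size.

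**5. After the fix**

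With glucose change limited to fasting samples, f = 0 and the bias against a fasting baseline is 0. Three of the 8 scheduled rows remain (Months 9 and 12 and Month 3 ExFU), 2 of them among the 6 on-treatment visits.

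**The case against.** The case for leaving the SAP alone is reasonable. The output is descriptive, with no hypothesis tests (SAP 4.2.5). Glucose is not singled out as an endpoint. The tables run by visit, so a rise at Months 7 and 8 followed by a fall at Month 9 could be noticed. All values are listed. The report covers all subjects whatever their treatment duration, and those who stopped early may have only Month 7 or 8 values, so restricting the tables loses their change data. A footnote on the fasting schedule would lose nothing.

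These arguments limit the weight of the point but do not remove it. A footnote leaves the change means and shift counts as they are, and the reader still cannot separate a meal from the drug.

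Four stronger readings are tempting, and the documents do not support them:

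- **That a spurious rise will appear.** Fasting is not required at the five visits, but it is not forbidden. Nothing shows how many subjects had eaten.
- **That every group is compared with a fasting baseline.** This is documented only for Baseline 2, and so for former placebo subjects.
- **That the SAP dropped the fasting schedule.** SAP Tables 1 and 2 reproduce it in footnotes. What is missing is a rule in 4.8.4 that uses it.
- **That a rise would count as an adverse event.** Under Protocol 12.1.2 an abnormal laboratory value is reported as one only if the investigator judges it clinically significant.

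**Conclusion.** The point holds as a defect in the laboratory tables. Followed as written, SAP 4.8.4 mixes fasting and possibly fed glucose in its change and shift summaries. For former placebo subjects this affects 4 of 6 on-treatment visits and Month 1 ExFU, which is off treatment; in all, 5 of 8 post-baseline chemistry visits. The conclusion assumes that Baseline 2 is the scheduled Month 6 draw and that at least some subjects had eaten at the other visits.

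The size of any resulting rise cannot be determined from the documents; the percentages above rest wholly on assumed inputs. For the two groups continuing active treatment, the same mismatch is plausible but depends on the fasting state of the main-study baseline, which is only suggested. No test or efficacy conclusion is affected. The change is worth making because it is cheap and alters tables that will be reported.

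**What to change.** In SAP 4.8.4, add a rule for glucose:

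- Base change from baseline, change from Baseline 2 and shifts on samples drawn under fasting conditions. These are the scheduled Month 9, Month 12 and Month 3 ExFU draws and discontinuation visits done under Month 12 procedures, with recorded fasting status used where available.
- Apply the same check to any sample reassigned to a visit under SAP 4.2.10, so that the rule follows the sample and not the visit label.
- Show all other glucose values separately as actual values, labelled as fasting not required, without change or shift. Keep every value in the listings.
- State the fasting condition of the main-study baseline draw, taken from the main study's own documents.

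As a separate wording correction, the opening of 4.8.4 says lipids were assessed at each visit from Month 7 to Month 12 and at Months 1 and 3 ExFU. Protocol 10.4.8 schedules them at Months 9, 12 and 3 ExFU only. The sentence should be aligned.

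The cost is SAP text, table footnotes and some programming to identify fasting samples; no new data are needed. The real loss is fewer glucose change rows, especially for subjects who stopped before Month 9 and have no fasting discontinuation sample.

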5.5.3 Safety

More than 1,500 subjects were exposed to a range of doses (25, 50, 75, 100, 200, 400 mg) of linzagolix from 13 completed and two ongoing clinical studies. Ongoing studies include two Phase 3 studies for the indication of heavy menstrual bleeding associated with uterine fibroids.

Repeated once daily dosing at up to 700 mg linzagolix was safe and well-tolerated by premenopausal healthy volunteers. In endometriosis patients, doses up to 200 mg once daily for up to 24 weeks of treatment were well tolerated.

Hepatic impairment had no relevant effect on total plasma linzagolix exposure. In women with severe hepatic impairment (Child-Pugh C), 2- to 3-fold unbound mean exposures were recorded. In hepatic impaired subjects, a single dose of 200 mg was well tolerated.

Renal impairment had no relevant effect on total plasma linzagolix exposure. In women with severe renal impairment (eGFR <30 mL/min/1.73 m2) or end-stage renal disease, approximately 2-fold

unbound mean exposures were recorded. In renal impaired subjects, a single dose of 200 mg was well tolerated.

The expected side effects of linzagolix are disturbances of the menstrual cycle and hypoestrogenic adverse events (AEs) (e.g., metrorrhagia and hot flush).

In multiple-dose studies, a dose-dependent occurrence of hot flush was observed (14.63%, 27.27%, 27.8%, 30% and 40.7% at 50 mg, 75 mg, 100 mg, 150 mg and 200 mg linzagolix, respectively). In the Phase 2b Edelweiss trial (15-OBE2109-001), a moderate proportion of patients reported a dose-dependent increase in hot flushes (at week 12, placebo: 10.9% reporting at least one hot flush; 75mg: 18.4%; 200 mg: 42.1% - at week 24, 75 mg: 19.0%; 200 mg: 45.6%).

Anticipated AEs are events that were not necessarily observed with linzagolix but can be anticipated based on the drug's pharmacological action and/or class effects, such as: increase in liver function test (LFT) parameters, headache, dizziness, nausea, hyperhidrosis, blood cholesterol increased, low density lipoprotein increased and BMD loss.

In few subjects, an increase in transaminase values exceeding 3>ULN (Upper Limit of Normal) was observed under treatment. Most often the increase in transaminase values was reversible and decreased spontaneously back to normal levels under treatment. Increases in transaminase values were not associated with increased bilirubin values.

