Liver function tests: following the Food and Drug Administration (FDA) guidance on drug-induced liver injury (8), subjects who have an elevation of hepatic enzymes are to be withdrawn immediately from treatment if:

- ALT or AST >8xULN
- ALT or AST >5xULN for more than 2 weeks
- ALT or AST >3xULN and (TBL >2xULN or INR >1.5)

• ALT or AST >3xULN with the appearance of fatigue, nausea, vomiting, right upper quadrant pain or tenderness, fever, rash, and/or eosinophilia (>5%)

Withdrawn subjects will be followed up until hepatic parameters return to normal.

ECG: subjects who have a QTcF > 500 ms or increase > 60 ms from the highest value prior to the first dose in the main study will have to be withdrawn from study treatment and followed up until return to QTcF < 480 ms or – if not reached after 3 months of treatment cessation- be referred to a cardiologist. They will enter the 6-month Follow-Up Period and undergo the follow-up ECGs according to the schedule of events.

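### The worst on-treatment ALT/AST value is classed only as Low, Normal or High, so that display cannot show the 3x, 5x or 8x ULN levels used in the hepatic withdrawal rules

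*SAP*

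**What the plan says.** SAP 4.8.4 (Laboratory Data) plans baseline shifts for all laboratory parameters, by normal range and by the normal / abnormal / abnormal clinically significant rating. It then singles out a liver group: "For Liver Function Test (LFT) parameters (ALT, AST, ALP, total bilirubin, direct bilirubin, indirect bilirubin, GGT, LDH, albumin and Creatine Kinase"). For these, the shift evaluation "will be extended by the worst (highest) on-treatment value (including unscheduled assessments"), classed "according to the normal ranges with categories" Low, Normal and High. The phrase occurs twice in the section, first in the general shift sentence. The liver sentence is the one at issue.

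The hepatic limits are set on another scale. Under Protocol 10.7.2.1, "subjects who have an elevation of hepatic enzymes are to be withdrawn immediately from treatment if" any of four criteria is met:

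- "ALT or AST >8xULN"
- "ALT or AST >5xULN for more than 2 weeks"
- ALT or AST above 3x ULN combined with total bilirubin (TBL) above 2x ULN or INR above 1.5
- ALT or AST above 3x ULN combined with listed symptoms or eosinophilia above 5%

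SAP 2.3.1 repeats these limits, and exclusion criterion 5d in Protocol 9.2.2 uses them for entry. As background, Protocol 5.5.3 records that in a few subjects "an increase in transaminase values exceeding 3>ULN (Upper Limit of Normal) was observed under treatment" (read here as three times ULN).

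**The concern.** A worst-value summary that includes unscheduled samples is meant to catch a peak that by-visit tables miss. Binning the peak by normal range shows that someone was above ULN but not by how much, and every liver limit in these documents depends on how much. Each parameter is also classed separately, so a transaminase rise with a simultaneous rise in bilirubin or INR cannot be seen.

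This matters more here than in the study as designed. After early termination, SAP 1.2 confines the analysis to safety, so the safety tables are the main summarised output. Protocol 5.7 names transaminase levels among the data for regular DMC review. Protocol 5.5.3 reports the sponsor's Phase 2b extension in multiples of ULN (no subject with AST or ALT above 2x ULN during that extension). The planned display could not support or refute a statement of that kind for this study.

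**Working it through.** No sample size, power or event count is involved. The check compares the planned classification with the limits and then looks for another planned table that fills the gap.

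**Step 1. What the bins separate.** The four values below are illustrative; each lies just above a boundary.

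| Worst ALT or AST | Planned class (SAP 4.8.4) | Class on the ULN scale |
|---|---|---|
| 1.1x ULN | High | >1-3x |
| 3.1x ULN | High | >3-5x |
| 5.1x ULN | High | >5-8x |
| 8.1x ULN | High | >8x |

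One planned class covers four ULN classes, so none of the 3x, 5x and 8x boundaries is visible.

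**Step 2. Which criteria can be read.**

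| Criterion (Protocol 10.7.2.1) | Planned display | ULN bins plus a joint count | Also needs a listing? |
|---|---|---|---|
| >8x | No | Yes, from the bins | No |
| >5x for more than 2 weeks | No | Level only, not duration | Yes |
| >3x with TBL >2x or INR >1.5 | No | Yes, from the joint count, given a timing rule | No |
| >3x with symptoms or eosinophilia | No | Level only, not symptoms | Yes |

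The planned display shows 0 of 4 criteria. ULN bins and a joint count show 2 of 4. The other two need dates of repeat samples, or adverse event and eosinophil data, for each subject.

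**Step 3. Other planned tables.** SAP 7.2 lists chemistry and coagulation tables separately: by visit, and shifts by clinical finding and by normal range. No title mentions multiples of ULN or a joint display of ALT/AST with bilirubin or INR. By-visit summaries include the maximum (SAP 4.2.1), but as an actual value and not as a multiple of ULN. Under SAP 4.2.10 an unscheduled value enters a visit only if it falls within 14 days of the theoretical date and that visit has no assessment, so a repeat or peak value can be left out.

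**Step 4. Comparison within the SAP.** SAP 4.8.3 gives BMD loss six classes, the last being a decrease above 8%, which is the BMD withdrawal limit in Protocol 10.7.2.1. SAP 4.8.4 gives LDL four categories and triglycerides five, although the discontinuation rules contain no lipid limit. ALT and AST, which carry four withdrawal criteria, have three classes, with all elevations in one of them.

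**The case against.** The strongest reply is that the information is not lost and that the SAP chose its format deliberately.

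- A crossing that led to withdrawal is reportable: Protocol 12.1.2 treats a laboratory abnormality that results in stopping IMP as clinically significant. It would count in the row for TEAEs leading to permanent discontinuation (SAP 4.8.2), appear in the by-subject listing of those events and contribute to the disposition table.
- Shifts by clinical significance give a second view of severity.
- All laboratory values are listed, with a subset listing of clinically significant ones.
- Because numbers are low, SAP 4.8.2 leaves even serious and related TEAEs to listings.
- Protocol 5.5.3 adds that most earlier transaminase rises reversed under treatment and were not accompanied by raised bilirubin.

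Most of this stands, and it limits the point. A reader might infer that the planned outputs as a whole cannot reveal a stopping-level liver event. The documents do not support that, because acted-on crossings surface as adverse events and every value is listed. Nor does the SAP plan a dedicated liver table that has gone wrong: the worst value is an extension of the chemistry shift evaluation, and Appendix B has no separate LFT table title. The SAP does not contradict the protocol either, since no protocol text requires tabulation by ULN multiple.

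What remains is narrower. The discontinuation row pools all causes. The clinical-significance rating is the investigator's judgement and not a ULN threshold. A crossing that was not acted on has to be found by hand: multiples must be computed from the listings, and chemistry must be joined to coagulation for the INR criterion. The chemistry and coagulation listing titles say central laboratory, while SAP 4.8.4 allows that some samples came from local laboratories; whether local results are included is not stated. Low numbers do not argue for the coarser bins, because the SAP keeps the worst-value evaluation regardless, and a clear zero above 3x ULN is itself informative.

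**Conclusion.** The point holds for this display. The worst-value liver shift cannot separate a trivial ALT or AST rise from one above 3x, 5x or 8x ULN, and none of the four hepatic criteria can be read from it. No planned table title indicates ALT/AST shown jointly with bilirubin or INR.

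The size is modest. It is a weakness of summary presentation in a SAP now centred on safety, with the data still available in listings and acted-on crossings visible as adverse events leading to discontinuation. How many subjects it would affect cannot be estimated, because the documents give neither the final number of subjects nor any liver results for this study.

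A reader might also infer that finer bins alone would make all four criteria readable. They would not, as step 2 shows. The conclusion assumes that the table titles in SAP 7.2 reflect the table contents, since no table shells are available. It takes the protocol's limits as given and does not question them.

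**What to change.** 1. For ALT and AST, class the worst on-treatment value, unscheduled assessments included, as <=1x, >1-3x, >3-5x, >5-8x and >8x ULN, using the ULN of the laboratory that ran the sample.
2. Add a count of subjects with ALT or AST >3x ULN together with TBL >2x ULN or INR >1.5. State the timing rule, for example same sample date. Without one, a peak ALT could be paired with a bilirubin or INR value from another date and create a false case.
3. Add a short listing of subjects meeting any of the four hepatic criteria in Protocol 10.7.2.1, because the 2-week and symptom criteria cannot be read from bins.

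This is a cheap improvement. The cut-points come from the protocol, the values and ULNs are already needed to assign High, and no data collection or trial conduct changes. The cost is a little extra programming for the joint count and the listing. Cells may be sparse given the low number of subjects, which is a further reason to pair the table with the listing.
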